3.3 Informed Consent Process

All participants will be provided a consent form describing the study with sufficient information for participants to make an informed decision regarding their participation. Participants must sign the IRB approved informed consent prior to participation in any study specific procedure. The participant will receive a copy of the signed and dated consent document. The original signed copy of the consent document must be retained in the medical record or research file.

3.4 Randomization Procedures

There is no randomization procedure.

3.5 Study Timeline

Primary Completion:

We estimate that the study will reach primary completion 36 months from the time the study opens to accrual.

Version #11, Date: 04-29-2015 Page 22 of 52

Study Completion:

We estimate that the study, including the up to 5 year long term follow up, will reach study completion 8 yearsthe time the study opens to accrual.

4. TREATMENT PLAN

4.0.1 Screening

The following procedures will be performed for all potential subjects at the Screening visit to be conducted 7 days prior to the start of Plerixafor infusion (+/- 3 days):

- Written informed consent must be obtained from the patient prior to performance of any study-specific tests or procedures
- Confirm Eligibility Criteria
- Post-operative, contrast-enhancing imaging
- Demographics: birth date, race/ethnicity and gender at birth
- Medical history
- Cancer history
- Physical Exam
- KPS
- Concomitant medications
- Vital Signs (including height and weight)
- ECG
- Laboratory tests: CBC with differential, Comprehensive Metabolic Panel (including: sodium, potassium, chloride, CO2, glucose, creatinine, urea nitrogen, calcium, protein, albumin, total bilirubin, ALK Phosphatase, AST, ALT and magnesium), Pregnancy Test (only for women of child bearing potential), INR, PTT, and Urinalysis with microscopic

Day 0 (within 3 days of beginning of Plerixafor infusion):

• Placement of the PICC line and infusion pump

Day 1 must occur 7 days (+/- 3 days) prior to the completion of XRT:

- Physical Exam
- KPS
- Vitals: pre-dose, 15 min (+/- 5 min), 30 min (+/- 5 min), 1 hr (+/- 15 min), 2 hrs (+/- 15 min) 3 hrs (+/- 30 min) and 6 hrs (+/-30 min) after the start of Plerixifor infusion
- Laboratory tests: CBC with differential, Complete Metabolic Panel (including: sodium, potassium, chloride, CO2, glucose, creatinine, urea nitrogen, calcium, protein, albumin, total bilirubin, ALK Phosphatase, AST, ALT and magnesium), Troponin
 - o Patients may proceed with the Plerixafor infusion even if the Day 1 ANC and platelets no longer meet inclusion criteria 3.1.7 due to the concurrent temodar and radiation and at the investigator's discretion; Thrombocytopenia should be ≤ grade 2
- Phase I only: SDF-1 levels (within 24 hours prior to the start of infusion)
- Phase I only: Samples for PK analysis will be drawn prior to and 1 hour (+/- 10 min) after start of the infusion of Plerixafor

Version #11, Date: 04-29-2015 Page 23 of 52

- ECGs: prior to the start of the Plerixafor infusion and 6 hours (+/- 30 min) after
- Phase I only: ECG 3 hours (+/- 30 min) after start of Plerixafor infusion
- Begin Plerixafor infusion in outpatient unit.
- Observe patients for 6 hours after the start of the Plerixafor infusion
- Patient will be discharged home after at least 6 hours with infusion pump.

Day 4 (+/- 2 days) for Phase I patients only

- Vitals
- Laboratory tests: CBC with differential, Complete Metabolic Panel (including: sodium, potassium, chloride, CO2, glucose, creatinine, urea nitrogen, calcium, protein, albumin, total bilirubin, ALK Phosphatase, AST, ALT and magnesium),
- ECG

Weekly following the start of the Plerixafor infusion through the end of infusion (+/- 3 days):

- Physical Exam
- KPS
- Vitals
- ECG
- Laboratory tests: CBC with differential, Complete Metabolic Panel (including: sodium, potassium, chloride, CO2, glucose, creatinine, urea nitrogen, calcium, protein, albumin, total bilirubin, ALK Phosphatase, AST, ALT and magnesium)
- Phase I only: PKs
- Change infusion bag of Plerixafor
- Review concomitant medications and adverse events
- On the last day of infusion, an SDF level will be checked (+/-1 week)
- Biweekly following the start of Plerixafor infusion through the end of infusion (+/- 3 days):Laboratory tests: Troponin

4 weeks after the end of XRT (+/- 7 days):

- MRI brain with and without contrast
- Start monthly TMZ

Concomitant medications and adverse events will be followed up until 30 days after the end of the Plerixafor infusion.

Investigator will manage monthly TMZ per their standard practice. Follow up MRIs will be done per standard of care (approximately every 8-12 weeks).

6 months after the start of XRT (+/- 2 weeks):

• MRI brain with and without contrast

Post-Progression Follow-Up:

Unless a patient has specifically withdrawn consent to be followed for survival, he or she will be

Version #11, Date: 04-29-2015 Page 24 of 52

contacted (by phone or clinic visit) every 12 weeks (+/- 2 weeks) following disease progression to collect data regarding survival status and subsequent anticancer therapy. Follow up will continue for either 5 years or until death, withdrawal, lost to follow up, or study termination.

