1. OBJECTIVES

1.1. Primary Objectives

- To assess the safety of using continuous infusion Plerixafor beginning one week prior to the end of concurrent chemotherapy with Temozolomide and radiation therapy in patients with newly diagnosed GBM.
- To assess the efficacy of Plerixafor as measured by progression free survival at 6 months (PFS6) from the start of irradiation.

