2.4 Study Design

For clinicaltrials.gov and Stanford Clinical Trials Directory compliance

- State the primary purpose for the protocol:
 - o Treatment
- State the interventional model from these choices:
 - Single Group
- State the number of intervention arms.
 - o One
- State whether the study will be masked (at least one party is unaware of the treatment)
 - o **Open**: no masking is used
- State whether the study is randomized.
 - o No
- State type of primary outcome or outcome that the protocol is designed to evaluate:

Safety (Phase I) Efficacy (Phase II)

Phase I

The Phase I is designed to evaluate safety. A total of 9 newly diagnosed patients will be enrolled within four weeks of surgery (biopsy, partial resection or gross total resection). In order to minimize the chances for local angiogenic migration into the irradiated field, irradiation will be administered to the area encompassed by T2 FLAIR imaging plus a 2 cm margin to 46 Gy with a focal boost to the enhancing area to 60 Gy over a six-week period. Temozolomide 75 mg/M²/d starting the day of radiotherapy will be administered for 42 days concurrent with irradiation. Eight days prior to irradiation completion, patients will have a PICC line placed. Seven days prior to irradiation completion, the continuous infusion of Plerixafor will be initiated using a step-wise dose escalation based on the modified toxicity probability interval (mTPI) method. All treatments will start one week prior to completion of radiotherapy with concurrent temozolomide for patients with newly diagnosed glioblastoma. This dose escalation study begins with an intermediate dose of 200 µg/kg per day for four weeks. The first 3 patients will be enrolled at this starting dose. Enrollment within a dose level will be staggered so that there is at least 1 week between patients. If tolerability and safety is established after the 4 week treatment period, then the fourth patient will be enrolled at the higher target dose of 400 µg/kg per day for four weeks. We will wait one week after the last infusion at one dose level before proceeding to the next dosage level.

If a patient experiences a DLT, then s/he will be removed from study and the next patient treated at the lower dose level as dictated by the mTPI table.

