3.1 Inclusion Criteria

- 3.1.1 Patients must have tissue confirmation of high grade (WHO Grade IV) glioma including but not limited to glioblastoma, gliosarcoma, glioblastoma with oligodendroglial features, glioblastoma with PNET features.
- 3.1.2 The patient must have post-operative contrast enhanced imaging (CT or MRI) unless only biopsy performed (in which case post-operative imaging is not routinely obtained. In these patients, the preoperative study will serve as baseline.
- 3.1.3 Patient should have surgery (biopsy, partial resection or gross total resection) and no additional anti-cancer therapy except the chemoradiation as specified in the protocol.
- 3.1.4 For those patients in which steroids are clinically indicated, there must be a stable or decreasing dose of steroid medication for \geq one week prior to the start of infusion.
- 3.1.5 Patients must be between the ages of 18 and 75 years old.
- 3.1.6 Patients must have Karnofsky Performance score ≥ 60 .
- 3.1.7 Adequate organ function is needed at time of screening visit including:
 - 1. ANC ≥ 1500
 - 2. Platelets > 100.000 ml
 - 3. Serum Creatinine ≤ 1.5mg/dl; Cr clearance should be > 50 mL/min
 - 4. AST and ALT \leq 3 times the upper limit of normal

Page 21 of 52

- 5. Serum potassium, magnesium and calcium within normal limits (supplementation to maintain normal electrolyte levels is acceptable)
- 6. If female of childbearing potential, negative pregnancy test
- 3.1.8 The patient or his/her legal representative must have the ability to understand and willingness to sign a written informed consent document.
- 3.1.9 Patient agrees to use an effective method of contraception (hormonal or two barrier methods) while on study and for at least 3 months following the Plerixafor infusion

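### Patients enter about four weeks into radiotherapy, but PFS6 runs from its first day against an unsourced 50% that is not conditioned on reaching that point, so the comparison leans modestly towards a positive result

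*Combined protocol and SAP*

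**What the plan says.** **Entry.** Section 4.0.1 has all potential subjects consented and checked for eligibility "at the Screening visit to be conducted 7 days prior to the start of Plerixafor infusion", with a window of 3 days either way. Consent is one of the visit's listed procedures: "Written informed consent must be obtained from the patient prior to performance of any study-specific tests or procedures". The study calendar (section 9) also marks consent at Day -7. The infusion date is tied to radiotherapy: "Day 1 must occur 7 days (+/- 3 days) prior to the completion of XRT". Section 2.4 gives the course as "to 60 Gy over a six-week period".

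**A different entry point.** For Phase I, section 2.4 says "A total of 9 newly diagnosed patients will be enrolled within four weeks of surgery".

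**Filters at entry.** Section 3.1 says "Adequate organ function is needed at time of screening visit including" a list of blood counts and chemistry limits. It also requires KPS of at least 60 and a steroid dose that has not risen in the week before infusion. Section 3.2 excludes bevacizumab. No criterion in 3.1 or 3.2 requires that the tumour has not already progressed.

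**Clock.** The primary objective in 1.1 is "progression free survival at 6 months (PFS6) from the start of irradiation". The outcome statement opening section 10, the definition in 10.2.2 and the MRI schedule in 10.2.4 use the same origin. Section 10.2.1 instead counts from completion of chemoradiation, and 12.2 counts from the start of an induction therapy that is not defined.

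**Comparator.** Sections 12.4, 12.5.2 and 12.7 expect at most 50% at 6 months and call the regimen of interest if the result is significantly higher. The synopsis asks only for more than 50%. Section 12.6.3 calls the comparator a historical control rate and gives no source, population or time origin. Twenty Phase II patients are planned for efficacy (12.5.1).

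**The concern.** When follow-up is counted from a date before entry, the time between the two dates can contain no deaths, because a patient who died then was never enrolled. Here that gap is about four of the 26 weeks. Patients whose KPS or blood counts are inadequate at screening, who have had a recent steroid increase, or who have been given bevacizumab also drop out before entry, and some of them would have been PFS failures. A historical rate counted from radiotherapy start in unselected patients includes those failures; the trial's denominator does not.

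The trial has one arm, and its recommendation for further study rests on this single comparison. Any mismatch of this kind pushes the estimate upward, towards a positive signal.

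**Working it through.** **1. When entry occurs.** Inputs: course 42 days (2.4); infusion start 7 ± 3 days before its end (4.0.1); screening 7 ± 3 days before infusion (4.0.1, section 9).
- Nominal: 42 − 7 − 7 = day 28.
- Earliest: 42 − 10 − 10 = day 22. Latest: 42 − 4 − 4 = day 34.

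**2. Consistency with section 2.4.** Enrolment within 28 days of surgery, with screening at radiotherapy day 22 or later, requires radiotherapy to start no more than 28 − 22 = 6 days after surgery. At the nominal day 28 it would have to start on the day of surgery (28 − 28 = 0), and for later screening days no start date works.

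**3. Expected PFS6 with an inactive drug.** The plan gives no figure for this, so there is none to reproduce. Assume that unselected PFS6 from radiotherapy start is exactly 50% and that everyone entering is event-free at entry. The second assumption is stricter than the eligibility criteria, so for deaths and progressions together it describes full exclusion of early events. With 6 months = 26.09 weeks and w the entry time in weeks:

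S(w) = 0.5^((w/26.09)^k), and conditional PFS6 = 0.50 / S(w).

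The shape k is an assumption, since the documents give no early hazard: k = 1 is a constant hazard, while k = 1.5 and k = 2 place fewer events early. At day 28, w = 4 and w/26.09 = 0.1533.

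| k | S(day 28) | PFS6, day 28 | PFS6, day 22 | PFS6, day 34 |
|---|---|---|---|---|
| 1 | 0.899 | 55.6% | 54.4% | 56.9% |
| 1.5 | 0.959 | 52.1% | 51.5% | 52.9% |
| 2 | 0.984 | 50.8% | 50.5% | 51.2% |

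The shift is +0.8 to +5.6 points at day 28 and +0.5 to +6.9 points over the visit windows. Without a hazard model, if 2% or 5% of patients fail before entry, the figures are 0.50/0.98 = 51.0% and 0.50/0.95 = 52.6%.

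**4. Chance of a false positive, n = 20, exact binomial.** The plan states no significance level, test or cut-off. Two rules bracket it: at least 11/20 (the synopsis rule) and at least 15/20 (assumed; the smallest count with one-sided probability at or below 5% when the true rate is 50%, since 14/20 gives 5.8%).

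| True rate | at least 11/20 | at least 15/20 |
|---|---|---|
| 50.0% (no selection) | 41.2% | 2.1% |
| 50.8% (k = 2, day 28) | 44.1% | 2.5% |
| 52.1% (k = 1.5, day 28) | 48.8% | 3.2% |
| 55.6% (k = 1, day 28) | 61.3% | 6.2% |

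**The case against.** **The time origin is not settled.** Section 10.2.1, which is specific to Phase II, counts from completion of chemoradiation. That is 42 − 28 = 14 days after nominal screening, so under it there is no lead time. This stands, and makes the point conditional. But 10.2.1 conflicts with the primary objective and with 10.2.2, so it shows that the origin must be fixed; it does not remove the mismatch under the primary definition.

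**Enrolment may precede radiotherapy.** Section 2.4 can be read that way, with Day -7 as a pre-infusion check. That sentence describes the nine Phase I patients. For the 20 Phase II patients the only stated timing is section 4.0.1 and the calendar.

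**Entrants are not guaranteed progression-free.** A reader might infer four weeks of guaranteed event-free time for every patient. The criteria do not support that. Steroids need be stable only for the week before infusion. KPS and counts are judged at screening, so a patient who dipped and recovered can enter, and 4.0.1 lets the infusion go ahead at the investigator's discretion when Day 1 counts no longer qualify. No MRI is scheduled between post-operative imaging and about 4 to 5 weeks after radiotherapy, so few radiological progressions would be recorded in the gap in any case. What is certain is survival to screening, plus indirect selection against early clinical failure.

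**The benchmark is unseen.** A reader might also infer that an inactive drug would be expected to beat 50%. The plan says at most 50%, for a composite that includes stable steroids and no bevacizumab. If the unselected rate were 44% (assumed), the constant-hazard model gives S = 0.44^0.1533 = 0.882 and 0.44/0.882 = 49.9% at day 28. If the 50% came from patients already selected at mid-radiotherapy, there would be no bias. The documents do not say either way.

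**Conclusion.** The mismatch holds under section 4.0.1, the calendar and the PFS6 origin in 1.1 and 10.2.2. Its direction is upward if the 50% comes from patients counted from radiotherapy start without the same selection. Its size is modest: about 51% to 56% expected at day 28 against a true 50%, or 50.5% to 56.9% over the visit windows. At the assumed 15/20 cut-off the false-positive chance stays near or below 5% for two of the three hazard shapes and reaches 6.2%, about three times the unselected 2.1%, under constant hazard. The 44% to 61% under the synopsis rule comes mostly from a rule that already gives 41% without selection.

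It would go too far to say that the efficacy question cannot be answered: a benchmark conditioned at the entry point would make the comparison like with like. The figures rest on assumed early hazards, an assumed cut-off and the 50% being the true unselected rate. Should-fix.

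**What to change.** 1. Reconcile the enrolment point across 2.4, 4.0.1 and section 9, for both phases.
2. Use one PFS6 origin in 1.1, section 10, 10.2.1, 10.2.2 and 12.2.
3. In 12.6.3, give the source, population and time origin of the 50%.
4. If late entry is kept, state in 12.4, 12.5.2 and 12.7 that PFS6 is conditional on being event-free at registration, and say how a patient with progression documented before registration is counted. Set the benchmark to 50% divided by the proportion of the benchmark population event-free at about radiotherapy day 28. That is about 51% to 56% under the hazards above; an observed proportion from the source is better than an assumed one.

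The cost is wording and a less favourable threshold. At 51% or 52% the assumed 15/20 cut-off still holds one-sided 5% (2.5% and 3.2%). At 55.6% it would move to 16/20 (exact 2.2%), and power at a true PFS6 of 75% among entrants would fall from 62% to 42%.

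Registering before the first fraction and counting everyone from then is an option, not a requirement. It removes the gap, but it changes the question to one that includes patients who never reach the infusion, and it reduces the number treated within a fixed 20.

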4.2 Criteria for Removal from Study

The investigator has the right to discontinue a patient from study drug or withdraw a patient from the study at any time. In addition, patients have the right to voluntarily discontinue study drug or withdraw from the study at any time, for any reason. Reasons for discontinuation or withdrawal include, but are not limited to:

- Patient withdrawal of consent
- Progression of disease by RANO criteria, as determined by the investigator
- DLT (any AEs with suspected causal relationship with Plerixafor >= grade 3 including ECG changes indicative of ischemia, ventricular tachycardia)
- Investigator decision (eg, symptomatic/clinical deterioration or not in the patient's best interest to continue in the study)
- Patient is lost to follow up
- Death
- Non-compliance of the patient with protocol mandated procedures
- Any unacceptable toxicity

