6.1 Dose Limiting Toxicities

DLT is defined as any hematologic or non-hematologic AE grade ≥3 with a suspected causal relationship to Plerixafor (including including ECG changes indicative of ischemia, ventricular tachycardia).

- Patients will be monitored for DLTs for 5 weeks from the start of the Plerixafor infusion.
- DLT's in the first cohort may occur before or after 14 days. If a DLT occurs in weeks 3 or 4 of treatment, we will treat next patient with a dose of 200 μg/kg/d x2 weeks. If a DLT occurs from the start of treatment through the second week of treatment, we will

Version #11, Date: 04-29-2015 Page 27 of 52

treat next patients at a dose of 100 μ g/kg/d x 4 weeks. If a patient experiences a DLT, the infusion will be discontinued. The next patient treated at the lower dose level as dictated by the mTPI table. If an early dose limiting toxicity occurs at lowest dose level (200 μ g/kg/d x 2 wk or 100 μ g/kg x 4wks) then the protocol will be stopped at that point.

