7. ADVERSE EVENTS AND REPORTING PROCEDURES

7.1 Potential Adverse Events

Safety will be assessed by monitoring clinical and laboratory evaluations and AEs.

Definitions

Adverse Event

An AE is any untoward medical occurrence associated with the use of the investigational product (active or placebo drug, biologic, or device) in a clinical investigation patient, which does not necessarily have a causal relationship with the investigational product. An AE can, therefore, be any unfavorable and unintended symptom, sign, disease or condition, or test abnormality whether or not considered related to the investigational product.

AEs may include, but are not limited to:

Subjective or objective symptoms spontaneously offered by the patient and/or observed by the investigator or medical staff

Clinically significant laboratory abnormalities

A significant worsening of the patient's condition from study entry

Disease signs and symptoms and/or laboratory abnormalities existing prior to the use of the study treatment that resolve but then recur after treatment

Disease signs and symptoms and/or laboratory abnormalities existing prior to the use of the study treatment which increase in frequency, intensity, or a change in quality after treatment

Version #11, Date: 04-29-2015 Page 28 of 52

Since prior studies using this medication have included premature ventricular contractions (PVCs), there will be a temporary interruption of plerixafor treatment for abnormalities in serum magnesium, calcium, or potassium at a Grade 2 or more severe. The study medication may be resumed following correction of these electrolyte abnormalities as confirmed by repeat serum level testing. Supplementation to include magnesium sulfate, calcium carbonate, or potassium chloride may be used as clinically indicated.

Serious Adverse Events (SAEs)

A SAE is any adverse event that results in any of the following outcomes:

- Death
- A life-threatening experience
- Requires inpatient hospitalization or prolongs existing hospitalization
- A persistent or significant disability/incapacity
- A congenital anomaly/birth defect
- Important medical events that may jeopardize the patient and may require medical or surgical intervention to prevent 1 of the outcomes listed above

Hospitalizations that occur under the following circumstances are not considered to be SAEs:

- were planned before entry into the clinical study;

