Describe all known or potential risks associated with this Investigational Drug/Device/Procedure. Include Adverse Event description, grade, expectedness, and attribution to the study treatment.

The most common adverse reactions ($\geq 10\%$) reported in patients who received Mozobil in conjunction with G-CSF regardless of causality and more frequent with Mozobil than placebo during hematopoietic stem cell mobilization and apheresis were diarrhea, nausea, fatigue, injections site reactions, headache, arthralgia, dizziness and vomiting. Per label (USPI) serious hypersensitivity reactions, including anaphylactic-type reactions, some of which have been life-threatening with clinically significant hypotension and shock, have occurred in patients receiving Plerixafor. In randomized studies, 34% of patients with non-Hodgkins's lymphoma and multiple myeloma had mild to moderate injection site reactions at the site of subcutaneous administration of Plerixafor. These included erythema, hematoma, hemorrhage, induration, inflammation, irritation, pain, paresthesia, pruritus, rash, swelling, and urticaria. Mild to moderate systemic reactions were observed in less than 1% of patients approximately 30 min after Plerixafor administration. Events included one or more of the following: urticaria (n = 2), periorbital swelling (n = 2), dyspnea (n = 1) or hypoxia (n = 1). Symptoms generally responded to treatments (e.g., antihistamines, corticosteroids, hydration or supplemental oxygen) or resolved spontaneously. Vasovagal reactions, orthostatic hypotension, and/or syncope can occur following subcutaneous injections. In Plerixafor oncology and healthy volunteer clinical studies, less than 1% of subjects experienced vasovagal reactions following subcutaneous administration of Plerixafor doses \leq 240 mg/kg. The majority of these events occurred within 1 hour of Plerixafor administration. Other adverse reactions that occurred in < 5% of patients but were reported as related to Plerixafor during mobilization and apheresis included abdominal pain,

Version #11, Date: 04-29-2015 Page 30 of 52

hyperhidrosis, abdominal distention, dry mouth, erythema, stomach discomfort, malaise, constipation, dyspepsia, and musculoskeletal pain.

In the study that assessed continuous infusion of Plerixafor over 10 days, four SAE's were noted: thrombocytopenia, infection of a PICC line and arrhythmia (> 25 PVC's/min) and panic attack associated with paresthesias [18].

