10.1.2 Measurement Definition

• The primary outcome is dose-limiting toxicity, which is defined as the absence of cardiac arrhythmia or grade III or IV adverse events.

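### Section 10.1.2 defines the DLT outcome in inverted form and in conflict with sections 6.1 and 4.2; as a smaller point, the Day 1 waiver in 4.0.1 caps thrombocytopenia but not neutropenia

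*Combined protocol and SAP*

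**What the plan says.** **DLT.** Section 6.1 states: "DLT is defined as any hematologic or non-hematologic AE grade ≥3 with a suspected causal relationship to Plerixafor". It adds ischaemic ECG changes and ventricular tachycardia as examples and sets the window: "Patients will be monitored for DLTs for 5 weeks from the start of the Plerixafor infusion". Section 4.2 uses the same two conditions for removal from study: "any AEs with suspected causal relationship with Plerixafor >= grade 3". Section 10.1.2, the measurement definition of the primary outcome, describes DLT differently: "which is defined as the absence of cardiac arrhythmia or grade III or IV adverse events". Section 12.1 sets out the escalation rules and the expansion-phase checks in terms of DLTs and gives no definition of its own. Section 12.2 tabulates qualifying DLTs without saying which definition qualifies them.

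**Day 1 counts.** Section 3.1.7 requires an ANC of at least 1500 and a platelet limit at the screening visit. For Day 1, section 4.0.1 relaxes both: "Patients may proceed with the Plerixafor infusion even if the Day 1 ANC and platelets no longer meet inclusion criteria 3.1.7". The shortfall must be due to the concurrent temozolomide and radiation, and the investigator must agree. One limit follows: "Thrombocytopenia should be ≤ grade 2". No limit for ANC is given there or elsewhere.

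**The concern.** The primary outcome of Phase I has two definitions, and one of them cannot be applied literally. If the dose is chosen by 6.1 and the outcome is reported by 10.1.2, the published DLT figure will not be the one that produced the recommended dose. Section 10 itself notes that each listed outcome measure carries a legal duty to report results, so its wording matters. If someone instead took 10.1.2 as the rule for dosing, events caused by temozolomide, radiation or the tumour, and low-grade rhythm findings, would enter a design of at most nine patients.

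The Day 1 point is separate and smaller. The waiver covers two blood counts and bounds one of them. Patients go home with a PICC line and pump for up to four weeks. Section 7.1 lists, among four serious events in an earlier ten-day continuous-infusion study, "thrombocytopenia, infection of a PICC line and arrhythmia". Starting such an infusion at grade 3-4 neutropenia adds infection risk. From grade 4, no worse grade of neutropenia can be observed.

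**Working it through.** **1. The definitions side by side**

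| Feature | 6.1 | 4.2 | 10.1.2 |
|---|---|---|---|
| Direction | presence of the event | presence of the event | absence of the event |
| Grade of general AE | 3 or higher, so 5 included | 3 or higher, so 5 included | III or IV only |
| Suspected causation by Plerixafor | required | required | not mentioned |
| Arrhythmia | ventricular tachycardia named, under the grade and causality conditions | same | any cardiac arrhythmia, no grade |
| Window | 5 weeks from start of infusion | not stated | not stated |

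**2. How three hypothetical patients would be classified**, with 10.1.2 read as presence:

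| Event | 6.1 | 10.1.2 |
|---|---|---|
| Grade 1 rhythm finding, possibly related | not a DLT | DLT |
| Grade 3 cytopenia attributed to temozolomide | not a DLT | DLT |
| Death from a non-arrhythmic event suspected to be related | DLT | not covered by the grades named |

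The definitions therefore disagree in both directions.

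**3. Which one drives dosing.** Section 6.1 goes from its definition directly to the de-escalation steps and to the mTPI table. Section 12.1 repeats those steps. Section 10 is introduced as text for registry compliance. The natural reading is that 6.1 sets the dose and 10.1.2 sets what is reported. No sentence says so.

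**4. What one counted event does.** Inputs from 12.1: Beta(1,1) prior, target 0.30 ± 0.05. The 0.95 cutoff for an unacceptably toxic dose is my assumption. With these settings every cell of Table 12.1 reproduces. For three patients, dividing the posterior probability of each interval by its width gives:

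- 0 of 3, Beta(1,4): below 0.25, 0.684/0.25 = 2.73; 0.25-0.35, 0.138/0.10 = 1.38; above 0.35, 0.179/0.65 = 0.27. Escalate.
- 1 of 3, Beta(2,3): 0.262/0.25 = 1.05; 0.175/0.10 = 1.75; 0.563/0.65 = 0.87. Stay.
- 2 of 3, Beta(3,2): 0.051/0.25 = 0.20; 0.076/0.10 = 0.76; 0.874/0.65 = 1.34. De-escalate (probability above 0.30 is 0.916, under 0.95).

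The table is sound. Its input is what has two definitions. One extra counted event among the first three patients changes escalate to stay, and two change it to de-escalate. In the expansion phase, one event in the first five patients triggers a toxicity review, which is not an automatic stop.

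**5. Whether the definitions could differ in practice.** By 4.0.1 the infusion starts 7 ± 3 days before radiotherapy ends, so 4 to 10 of the 35 DLT days (4/35 = 11% to 10/35 = 29%) overlap chemoradiation. ECGs are taken on Day 1, on Day 4 in Phase I, and weekly. Section 7.1 mentions premature ventricular contractions in earlier studies. Section 2.5 reports grade 1 sinus tachycardia in most volunteers at 400 and 480 µg/kg. Those were single doses; here 400 µg/kg is spread over 24 hours, or 400/24 = 16.7 µg/kg/h. This shows that such events can occur. It gives no rate for this regimen.

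**6. Day 1 neutrophils.** Screening is 7 ± 3 days before the infusion, so the ANC of at least 1500 was measured 4 to 10 days earlier. Section 6 allows no dose modification or delay except for renal impairment. The only laboratory-triggered interruption, in 7.1, is for magnesium, calcium or potassium. Section 4.1 permits antimicrobial prophylaxis without requiring it. Nothing in the text therefore bars a start at grade 3-4 neutropenia.

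**The case against.** The strongest reply on DLT is that no one would be misled. Section 6.1 carries the DLT heading, sets the window and points to the mTPI table; 4.2 agrees; and 10.1.2 cannot be used literally because of the word absence. This stands as far as dosing goes. A reader might infer that escalation would run on the wrong events, or that patients would be kept from the target dose. The documents do not support that: 6.1 is the natural dosing rule, and they give no rate for events that count only under 10.1.2. The reply does not settle what is reported as the primary outcome.

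On Day 1 counts, the missing ANC limit may be deliberate. Section 4.0.1 expressly leaves ANC, like platelets, to the investigator and ties the waiver to chemoradiation. Section 2.5 reports that Plerixafor raises white cell counts. Blood counts and physician review are weekly. The PICC infection cited in 7.1 arose in a study of HIV patients and gives no rate here. All of this stands and makes the event probably rare. A reader might also infer that neutropenic starts would hide DLTs on a scale that matters. That goes too far: a grade 3 or higher infection or febrile neutropenia with suspected causation by Plerixafor would still count under 6.1. What remains is that the authors set a limit for platelets despite the same discretion, and none for neutrophils.

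**Conclusion.** The DLT point holds as an error in the text. Section 10.1.2 is inverted, drops causality, admits arrhythmia of any grade, omits grade 5 and so contradicts 6.1 and 4.2. The expected consequence is a mismatch between the reported primary outcome and the DLT count behind the chosen dose. An effect on dosing follows only if 10.1.2 is used for that purpose. In that case a single event can change an early decision among nine patients, but no probability can be attached from these documents. The conclusion assumes that 6.1 is the intended dosing rule.

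The Day 1 point holds as a minor safety improvement. The protocol permits a start at grade 3-4 neutropenia, subject to investigator judgement. The frequency is not stated and is probably low.

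**What to change.** 1. Replace the sentence in 10.1.2 with the 6.1 definition: a haematologic or non-haematologic adverse event of grade 3 or higher, suspected to be caused by Plerixafor, occurring within 5 weeks of the start of infusion. State there or in 12.1 that this definition feeds Table 12.1 and the expansion-phase checks. Tabulate arrhythmia of any grade separately as a safety summary. This needs no extra data, visits or patients.

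2. In 4.0.1, extend the Day 1 limit so that thrombocytopenia and neutropenia must each be grade 2 or lower. The CBC with differential is already drawn on Day 1. The cost is that an occasional patient may not start unless the count recovers within the Day 1 window, possibly with the PICC already placed. Taking the CBC before line placement, where feasible, reduces that.
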